6.7.2 Effectiveness Analyses

6.7.2.1 Primary Effectiveness Analyses

Primary effectiveness analyses will be performed per cohort and per sub-cohort, at the eye-level, for the EFAS-EL.

The primary effectiveness endpoint is the change in VA (approximate ETDRS letter score) from index date to month 12 per nAMD and DME and per treatment naïve and pre-treated sub-cohorts. VA will be measured as per the local practice at index date and at month 12. To allow statistical analysis of the different clinical methods used to measure VA, the assessments will be automatically converted to the approximate ETDRS letter score. The approximate ETDRS letter score conversion table can be found in [Appendix 3](#).

Both actual values at index date and month 12 and change from index date in VA (approximate ETDRS letter score) to month 12 will be summarized descriptively.

6.7.2.2 Secondary Effectiveness Analyses

Secondary effectiveness analyses will be performed on eye-level per cohort (nAMD/DME) and per sub-cohort (treatment naïve and pre-treated eyes) for the effectiveness dataset (EFAS-EL).

Change in VA (approximate ETDRS letter score) will be estimated from index date to months 3, 6, 24.

Actual VA values as well as change from index date in VA (approximate ETDRS letter score) will be summarized descriptively and graphically at index date, months 3, 6, and 24. Change in VA will also be described according to treatment regimen (Fixed, T&E, PRN, Other), number of intravitreal treatments, total number of visits, time interval between treatments, pre-treatment type (specified therapeutic) and number of previous injections for preceding regimen at index date.

In addition, mean change in VA from index date to month 12 will be estimated using Mixed Model for Repeated Measurement (MMRM). The model will use all the data collected up until the point of analysis. Complete model specifications will be detailed in the SAP.

Both actual values and change from index date in CST will be summarized descriptively at index date, months 3, 6, 12 and 24 using mean, median, SD, first quartile, third quartile, minimum, and maximum.

The number and percentage of eyes in each treatment regimen (i.e., Fixed regimen, T&E, PRN, Other) will be calculated and summarized at index date, months 3, 6, 12 and 24.

The number and percentage of treatments (faricimab injections) received in each eye, from index date to months 3, 6, 12, 24 will be calculated and summarized by study cohort and pre-treatment type.

The number of faricimab intravitreal treatments (on eye-level), per year, per nAMD and DME, and per treatment naïve and pre-treated sub-cohorts will be calculated and summarized descriptively using mean, median, SD, first quartile, third quartile, minimum, and maximum.

Total number of visits (with or without treatment) and time interval between treatments, per year, per nAMD and DME, and per treatment naïve and pre-treated sub-cohorts will be summarized descriptively using mean, median, SD, first quartile, third quartile, minimum, and maximum.

The number of loading dose intravitreal injections in treatment naïve and pre-treated patients (per pre-treatment type) by nAMD and DME will be calculated and summarized.

Cumulative time spent in each treatment regimen (i.e., Fixed regimen, T&E, PRN, Other), per nAMD and DME, and per treatment naïve and pre-treated sub-cohorts will be summarized descriptively using mean, median, SD, first quartile, third quartile, minimum, and maximum.

The number and percentage of eyes obtaining treatment intervals of Q8W, Q12W, Q16W and other at 12 months and 24 months will be calculated and summarized by study cohort and for treatment naïve and pre-treated patients (by pre-treatment type).

The number and percentage of eyes discontinuing faricimab treatment in each cohort will be calculated at months 3, 6, 12, and 24 (the reason for treatment discontinuation will be reported at the same time periods).

The number and percentage of eyes switching treatment regimen or treatment type and reason for switch at months 3, 6, 12 and 24 will be calculated and summarized per nAMD and DME.

Time to first treatment switch will be calculated per nAMD and DME and summarized using Kaplan-Meier estimate.

Number and percentage of eyes switched from faricimab to a non-faricimab product will be calculated and summarized at index date, months 3, 6, 12 and 24.

Number, type and frequency of ocular concomitant and subsequent medications received during the study period will be calculated and summarized descriptively by eye.

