B. Pre-treated sub-cohort: Patient-eyes newly initiating faricimab intravitreal treatment* after being previously treated with intravitreal anti-VEGF	B. Pre-treated sub-cohort: Patient-eyes newly initiating faricimab intravitreal treatment* after being previously treated with intravitreal anti-VEGF

DME = diabetic macular edema, nAMD = neovascular age-related macular degeneration, VEGF = vascular endothelial growth factor

*Patient-eyes newly initiating faricimab intravitreal treatment: patient-eyes initiated treatment during 3 months prior to enrollment.

Patients may be part of several sub-cohorts as analysis will be carried out at eye-level (regardless of whether it is the right or left eye).

Unless otherwise specified, statistical analyses will be performed per cohort and per sub-cohort.

Patients' demographics as well as medical history (ocular and non-ocular) will be summarized using descriptive statistics. Baseline ocular characteristics and information on prior ocular treatments will be summarized descriptively.

Patient and eye disposition (e.g., enrolled, treated, switched therapy, early discontinuation, study completers) will be summarized using the Safety Analysis Sets.

Continuous variables will be summarized descriptively using mean, median, standard deviation (SD), first quartile, third quartile, minimum, and maximum. Categorical outcomes will be summarized using numbers and percentages in each category.

The primary effectiveness endpoint is the change in VA (approximate ETDRS letter score - see [Appendix 3](#)) from index date to month 12 in nAMD and DME. Both actual values at index date and month 12 and change from index date in VA (approximate ETDRS letter score - see [Appendix 3](#)) to month 12 will be summarized descriptively.

The key secondary endpoints are the change in VA (approximate ETDRS letter score - see [Appendix 3](#)) from index date to months 3, 6, and 24 in nAMD and DME, and the change in CST from index date to months 3, 6, 12 and 24 (as measured per local standard clinical practice). All primary, secondary and exploratory effectiveness outcomes will be analyzed using the Effectiveness Analysis sets.

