6.7.1.2 Effectiveness Analysis Set

Patient-Level

The Effectiveness Analysis Set - Patient-Level (EFAS-PL) will consist of patients who meet all inclusion and none of the exclusion criteria, and who received at least one dose of faricimab in nAMD of DME indications and provide data for VA at least at the index date and one post-index visit.

Eye-Level

The Effectiveness Analysis Set - Eye-Level (EFAS-EL) will consist of eyes with indication and treatment in scope of the study from patients who meet all inclusion and none of the exclusion criteria, and who received at least one dose of faricimab in nAMD or DME indications, with VA measurements at least at the index date and one post-index visit.

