6.7.4.2 Specific Exploratory Analyses for Health Economic Perspective

Exploratory analyses for health economic perspective will be performed per cohort (nAMD, DME) and per sub-cohort (treatment naïve and pre-treated), at the eye-level, based on effectiveness dataset.

The following will be calculated for anti-VEGF pre-treated eyes (pre-treated sub-cohorts) in nAMD and DME and summarized descriptively:

- Type of anti-VEGF treatments received before index date
- Time spent on each pre-treatment
- Number of previous injections for previous treatment
- Treatment interval of the last preceding treatment before entering the study.

The following will be collected prospectively starting at index date, calculated per cohort (nAMD, DME) and sub-cohort (treatment naïve and pre-treated) and summarized descriptively (at index date, 3, 6, 12, 24 months):

- Number and percentage of eyes in each treatment regimen (i.e., Fixed regimen, T&E, PRN, Other).
- Number of injections per eye per year.

- Total number of visits (per eye per year)
- Number of visits with treatment (per eye per year)
- Number of visits without treatment (observational) per eye per year
- Time intervals between treatments, per eye per year.

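### Treatment-pattern, discontinuation and switch endpoints that do not use VA are placed on a VA-conditioned eye set; discontinuation is likely understated, and the sections disagree on the set

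*Protocol*

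**What the plan says.** The header of section 6.7.2.2 assigns the secondary analyses to the eye level, per cohort and "per sub-cohort (treatment naïve and pre-treated eyes) for the effectiveness dataset (EFAS-EL"). The synopsis states the same rule: "All primary, secondary and exploratory effectiveness outcomes will be analyzed using the Effectiveness Analysis sets".

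The items under that header include change in VA and CST, but also regimen, injections per year, visits and loading injections. They further include:

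- Discontinuation: "The number and percentage of eyes discontinuing faricimab treatment in each cohort will be calculated at months 3, 6, 12, and 24".
- Switch: "Time to first treatment switch will be calculated per nAMD and DME and summarized using Kaplan-Meier estimate".
- Durability: "The number and percentage of eyes obtaining treatment intervals of Q8W, Q12W, Q16W and other at 12 months and 24 months".

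No item is exempted. Section 6.7.4.2 runs the health-economic tables, including pre-treatment history, "at the eye-level, based on effectiveness dataset".

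Section 6.7.1.2 admits an eye to EFAS-EL only "with VA measurements at least at the index date and one post-index visit". Section 6.7.1.1 defines SAS-EL, identical to EAS-EL, as the treated eyes in scope with no VA condition.

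Two other places use the safety sets for overlapping content. The synopsis says: "Patient and eye disposition (e.g., enrolled, treated, switched therapy, early discontinuation, study completers) will be summarized using the Safety Analysis Sets". Section 6.7.4.3 summarises ocular concomitant medications on SAS-EL, although the last item of section 6.7.2.2 puts them under the EFAS-EL header.

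**The concern.** A VA condition suits an endpoint computed from VA. It has no role in whether an eye stopped faricimab, how many injections it had, or what it received before the index date.

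Here the condition is also tied to the outcome. Section 6.1.1 mandates no visits and no additional tests, so a later VA exists only if the patient returned and acuity was recorded. Section 6.5.1 lists no longer attending the site, adverse events and death among the reasons for leaving the study. Eyes lost that way soon after the first injection drop out of both numerator and denominator.

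Treatment patterns and durability are named secondary objectives in section 5.2.1. They would be answered in eyes partly selected for having stayed, while Table 1 collects switch and discontinuation dates and reasons by eye with no VA condition. A reader would also meet switch figures on two denominators without explanation.

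**Working it through.** The protocol states no figure for this point, so there is none to reproduce. The sizes below are illustrations.

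**Inputs.** From the protocol: the EFAS-EL entry rule (6.7.1.2), the SAS-EL definition (6.7.1.1) and the set assignments (6.7.2.2, 6.7.4.2, 6.7.4.3, synopsis). Assumed, because the documents do not give them:

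- e, the share of treated eyes excluded from EFAS-EL: 2%, 5%, 10%. The only nearby figure is the 5% drop-out in section 6.7.6, which is not the same quantity.
- D, true discontinuation among treated eyes: 15%.
- s, the share of excluded eyes that discontinued: from D up to 100%.

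**Step 1: who is excluded.** The entry rule has no time window and no on-treatment condition. Only eyes with no index VA, or with no post-index VA ever recorded, are dropped.

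**Step 2: discontinuation.** The EFAS-EL figure is (D − s·e)/(1 − e). It falls below D exactly when s > D, that is, when excluded eyes stopped more often than treated eyes overall. With D = 15%:

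| e | s = 100% | s = 50% | s = D |
|---|---|---|---|
| 2% | 13/98 = 13.3% | 14/98 = 14.3% | 15% |
| 5% | 10/95 = 10.5% | 12.5/95 = 13.2% | 15% |
| 10% | 5/90 = 5.6% | 10/90 = 11.1% | 15% |

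**Step 3: injection counts.** With an assumed mean of m = 6.5 per year over all treated eyes and k = 1 in excluded eyes, EFAS-EL shows (m − e·k)/(1 − e). At e = 5% this is 6.45/0.95 = 6.8. The direction assumes counts per eye within the year, not counts divided by a short observed time.

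**Step 4: interval categories.** If a share Q of all treated eyes is at Q16W and the denominator is every eye in the set, EFAS-EL shows Q/(1 − e). With an assumed Q = 50%, that is 51.0%, 52.6% or 55.6% for e = 2%, 5% or 10%. If the denominator is eyes with an interval at that month, eyes lost early count under neither set and nothing changes. The protocol does not say which applies.

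**Step 5: switch.** A switched eye has normally returned for another treatment and probably has a later VA. An eye lost early would be censored early in the Kaplan-Meier estimate and contribute little. The expected effect is small.

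**Step 6: what SAS-EL recovers.** In the case e = 5%, s = 100%, SAS-EL restores 15% only if the excluded eyes have a recorded discontinuation. If none has, SAS-EL shows 10/100 = 10.0%, against 10.5% on EFAS-EL. Changing the set alone is then not enough.

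**Step 7: set assignments side by side.**

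| Content | Under 6.7.2.2 | Elsewhere |
|---|---|---|
| Switch from faricimab | EFAS-EL | Safety Analysis Sets (synopsis, disposition) |
| Ocular concomitant medications | EFAS-EL | SAS-EL (6.7.4.3) |
| Discontinuation of faricimab | EFAS-EL | Possibly the Safety Analysis Sets (synopsis), if early discontinuation means treatment |

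**The case against.** A reader might infer that EFAS-EL removes every eye that stops before its second VA. The documents do not support that. Sections 6.1.1 and 6.5.2 keep patients in the study after they stop or switch faricimab, and section 6.3.1 collects all available VA measurements, so a later routine VA brings the eye back in. Enrollment may also follow the first injection by up to 3 months, so some eyes already have a post-index VA at entry. Both facts reduce the size.

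A reader might also infer that discontinuation is certainly biased low and durability certainly biased high. Neither is shown. Some excluded eyes need not have stopped, such as a second eye started late or an eye lacking an index VA. Durability depends on an unstated denominator.

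The synopsis already plans a disposition summary on the safety sets, so a switch figure on all treated eyes will exist. Its early-discontinuation item stands next to study completers and may mean leaving the study. The study is descriptive and the primary VA endpoint is not affected.

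All of this limits direction and size. It does not justify a VA condition on endpoints that do not use VA. Nor does the protocol promise the disposition summary by month or as a Kaplan-Meier estimate, so it does not replace the endpoints in section 6.7.2.2.

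**Conclusion.** The point holds in a limited form. The protocol fixes the set explicitly, so this is not a detail left to the SAP. The set is unsuited to the non-VA endpoints, and the assignments conflict for switched therapy and for ocular concomitant medications.

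The likely effects are understated discontinuation and overstated injection counts, provided that excluded eyes stopped more often and were injected less than treated eyes overall. That is plausible because entry depends on returning, but the documents do not demonstrate it. For pre-treatment history, which is complete before the index date, the rule discards usable data without a clear direction of bias.

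The size cannot be derived. With 15% true discontinuation assumed, the shortfall runs from 0 to 4.5 points (15 − 10.5) at 5% excluded, and from 0 to 9.4 points (15 − 5.6) at 10% excluded. The upper ends require every excluded eye to have discontinued.

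**What to change.** 1. In sections 6.7.2.2 and 6.7.4.2, keep EFAS-EL for VA-based endpoints. State that regimen, injection counts, visits, interval categories, discontinuation, switch, time to switch and the health-economic tables are analysed on SAS-EL (= EAS-EL).
2. Align the two synopsis sentences on analysis sets and section 6.7.4.3 with this, and say whether early discontinuation in the disposition summary means treatment or study.
3. For regimen and interval percentages at each month, keep all eyes of the set in the denominator and show switched, discontinued and lost-to-follow-up eyes as separate categories. This makes the durability denominator explicit and shows eyes lost without a recorded discontinuation, which the change of set alone would not reveal.

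The cost is about one sentence per section plus extra table rows, with no new data. The percentages may look slightly less favourable.

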6.7.3 Safety Analyses

The Safety Population will consist of all consented patients who receive faricimab in nAMD and DME. Summary tables and listings will be based on the Safety Population (SAS-EL or SAS-PL).

The Safety Endpoint is the incidence of ocular and non-ocular AEs.

Non-ocular AEs/serious adverse events (SAEs) will be assessed at patient-level, per cohort and per sub-cohort, for the SAS-PL.

Ocular AEs/SAEs will be assessed at eye-level, per faricimab and any other anti-VEGF treatment, per cohort (nAMD, DME) and per sub-cohort (treatment naïve and pre-treated eyes), for the SAS-EL.

The incidence of AEs/SAEs will be summarized descriptively by Medical Dictionary for Regulatory Activities (MedDRA) Primary System Organ Class (SOC) and Preferred Term (PT). Cumulative incidence and rates per 100 patient-years or 100 patient-eye years (for eye-level events) (or per 1,000 patient-years, etc., as appropriate) of AEs and SAEs will be calculated.

The number and percentages of patients (or eyes) experiencing AEs and SAEs as well as the number of events will be displayed by SOC, PT, and by severity. AE outcome and duration of AE will be summarized descriptively. For all outcome measures, events with onset through end of study will be summarized at the final analysis.

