6.7.1.1 Enrolled Analysis Set / Safety Analysis Set

Patient-Level

The Enrolled Analysis Set/Safety Analysis Set- Patient-Level (EAS-PL, SAS-PL) will consist of patients who meet all inclusion and none of the exclusion criteria, and who received at least one dose of faricimab in nAMD of DME indications.

Eye-Level

The Enrolled Analysis Set/Safety Analysis Set - Eye-Level (EAS-EL, SAS-EL) will consist of eyes with indication and treatment in scope for this study from patients who meet all inclusion criteria and none of the exclusion criteria, and who received at least one dose of faricimab in nAMD of DME indications.

The Enrolled Analysis Sets in this study are identical to the corresponding Safety Analysis Sets, because according to the inclusion criteria, only patients who have received at least one faricimab injection at enrollment or prior to enrollment can be included in the study.

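### Protocol sections 6.7.3 and 6.7.1.1 give the safety analysis sets two different memberships; read literally, 6.7.1.1 removes treated patients with an eligibility deviation from the adverse event tables

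*Protocol*

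**What the plan says.** Protocol section 6.7.3 (Safety Analyses) opens with a definition that carries no eligibility condition: "The Safety Population will consist of all consented patients who receive faricimab in nAMD and DME". The next sentence ties this population to the named analysis sets: "Summary tables and listings will be based on the Safety Population (SAS-EL or SAS-PL"). The section then assigns tables to those sets, for example "Non-ocular AEs/serious adverse events (SAEs) will be assessed at patient-level, per cohort and per sub-cohort, for the SAS-PL". Ocular events go to SAS-EL in the same way.

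Section 6.7.1.1 defines the same sets differently. At patient level the set "will consist of patients who meet all inclusion and none of the exclusion criteria" and who had at least one dose. At eye level it takes in-scope eyes "from patients who meet all inclusion criteria and none of the exclusion criteria, and who received at least one dose of faricimab". The section adds: "The Enrolled Analysis Sets in this study are identical to the corresponding Safety Analysis Sets". The reason given is that "only patients who have received at least one faricimab injection at enrollment or prior to enrollment can be included in the study".

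**The concern.** Two sentences in one protocol decide who enters the safety tables, and they disagree about one group: patients who consented, were treated and enrolled, and are later found to have breached an entry criterion. Section 6.7.3 keeps them; 6.7.1.1 removes them. The numerator and denominator of each adverse event percentage, cumulative incidence and rate per patient-year or eye-year can depend on which sentence is programmed.

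Leaving detail to the SAP does not settle this. The protocol has not left the set open; it has fixed it twice, so a SAP can follow only one version and will contradict the other. Safety is a stated objective (section 5.2.2), and treated patients would normally be counted whether or not they should have been enrolled.

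**Working it through.** The protocol has no figure of its own to reproduce on this point. The check compares the two definitions as sets, then counts under a stated assumption.

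**1. The two sets**
- B (6.7.3): consented and treated with faricimab.
- S (6.7.1.1): treated, every inclusion criterion met, no exclusion criterion met.
- Consent is part of inclusion criterion 1 (section 6.2), so S lies within B. The difference, B minus S, is the consented, treated patients with at least one eligibility deviation. It is empty only if there are none.

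**2. Does the stated reason for EAS = SAS close the gap?** No. It says that everyone included has had an injection. That deals with the dosing condition and is silent on breaches of the other criteria.

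**3. Where do the removed patients appear?**
- Enrolled sets: same clause, so absent.
- Effectiveness sets (6.7.1.2): same clause, so absent.
- Disposition: the Synopsis (Data Analysis) bases it on the Safety Analysis Sets, so absent there too, and the loss would not show.
- Eye level: the clause applies to the patient, so one breach removes every eye of that patient.
- Data collection: section 8.1.2.1 collects adverse events from index date for any enrolled patient, with no eligibility condition. The data would exist but enter no table.

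**4. How many?** Inputs: about 850 patients, 600 with nAMD and 250 with DME, the smallest sub-cohort being 100 treatment-naïve DME patients (6.1.3). The deviation rate f is an assumption, 1% to 5%, taken as equal across cohorts. Number removed = N × f.
- All: 850 × 0.01 = 8.5; 850 × 0.05 = 42.5 (about 9 to 43)
- nAMD: 600 × 0.01 = 6; 600 × 0.05 = 30
- DME: 250 × 0.01 = 2.5; 250 × 0.05 = 12.5
- Treatment-naïve DME: 100 × 0.01 = 1; 100 × 0.05 = 5
- f = 0: none, and the definitions coincide.

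**5. Which direction?** Let p_d be the event proportion in the removed patients and p_r that in the retained ones. The full-set proportion is (1 − f)p_r + f·p_d. The stricter rule reports p_r, so it understates by f(p_d − p_r). The sign depends on whether removed patients have more events than the rest, and the protocol gives neither proportion.

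There is one route to p_d > p_r. Enrollment cannot precede index date (6.1.1), and treatment may have begun up to 3 months earlier (6.2), so the exclusion criteria are applied after at least one injection. Criterion 3 covers active ocular inflammation or infection, and criterion 7 covers hypersensitivity. A patient who developed such a condition after the first injection and was enrolled in error has a deviation that is also a possible adverse event within the collection period. The stricter rule would remove that event.

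**The case against.** The best counter-argument is that only one set is really meant. Section 6.7.3 points to SAS-EL and SAS-PL, so its first sentence may be a loose paraphrase of 6.7.1.1. The remark that the enrolled and safety sets coincide suggests the authors had everyone enrolled in mind, and no sentence says outright that a patient is deleted after enrollment. That may well be the intent, but the eligibility clause is still there in 6.7.1.1, and a programmer who follows it would exclude these patients.

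Other parts of the objection stand:
- The criteria govern study entry. Inflammation or hypersensitivity arising after enrollment is an adverse event, not a deviation, and counts under both rules. A patient correctly refused entry appears under neither. Only patients enrolled in error with the condition present at entry are affected by the bias route.
- Other criteria, such as participation in another study or in a support program, have no evident link to adverse events in one direction.
- Reporting to the marketing authorization holder (8.1.3.1, 8.1.3.2) has no eligibility condition. The events are not lost; only the aggregate analyses and listings are affected.
- The study is descriptive, and none of its stated figures depends on this point.

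A reader might go further and infer that the stricter rule understates serious ocular harm by a quarter or a third. That takes inputs the protocol does not supply. Suppose 1% incidence, so 8.5 events in 850, and suppose 2 to 3 of those events fall among the 2% to 5% removed (17 to 42.5 patients). Incidence then becomes between 6.5/807.5 = 0.81% and 5.5/833 = 0.66%, a relative fall of 20% to 34%. But this puts the event proportion in the removed patients at 2/42.5 = 4.7% to 3/17 = 17.6%, about 6 to 27 times that in the rest, with nothing to support it. If the removed patients had the same 1% as everyone else, 0.17 to 0.43 events would go and the incidence would not change.

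**Conclusion.** The contradiction is real and sits wholly within the protocol: the same named sets are defined with an eligibility condition in 6.7.1.1 and without one in 6.7.3. Under the literal 6.7.1.1 rule, treated patients with a deviation, and all their eyes, leave the safety tables and disposition. The number affected is about 9 to 43 of 850 if 1% to 5% have a deviation, which is an assumption; it is zero if nobody does.

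Bias towards fewer events is possible through exclusion criteria 3 and 7. The documents do not support a claim that harm is understated in general, nor any percentage for it. This is a correction of wording, best made before the first annual exploratory interim analysis (6.7.5) so that all reports use one denominator.

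**What to change.** In section 6.7.1.1, remove the eligibility clause from both the Enrolled and the Safety Analysis Sets. Define them as all consented, enrolled patients (patient level), or their in-scope eyes (eye level), with at least one faricimab injection for nAMD or DME, regardless of eligibility deviations. Replace the opening sentence of 6.7.3 with a reference to that definition. If an eligibility restriction is wanted, keep it in the effectiveness sets (6.7.1.2) only.

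Keep the sentence that the enrolled and safety sets are identical. Inclusion criterion 3 already requires an injection, so it stays true once both sets are changed. Widening the safety sets alone would leave safety-set patients outside the Enrolled set.

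The cost is wording in the protocol, and in the SAP if it repeats the clause, plus the submission steps in section 3 for an amendment. No new data are needed. The safety set becomes slightly larger and less clean.

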5.2.2 Safety Objective

Safety Objective	Safety Analysis
To evaluate the ocular and systemic safety and tolerability for faricimab in nAMD and DME in the real-world setting.	
 Incidence, severity, duration, and outcomes of ocular and non-ocular adverse events.

DME = diabetic macular edema, nAMD = neovascular age-related macular degeneration

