6.5.2 Discontinuation from Treatment with Studied Medicinal Product

The decision for treatment discontinuation lies with the treating physician and is not regulated by this protocol.

If a patient discontinues from faricimab treatment or switches to another treatment, even if faricimab is not being received in either eye, the patient should continue to participate in this study until the end of study participation (defined in [Section 6.1.1](#)).

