8.1.2.1 Adverse Event Reporting Period

Qualified HCPs will seek information on AEs at each patient contact. All AEs subject to the collecting and reporting requirements outlined in this protocol, whether reported by the patient or noted by study personnel, will be recorded in the patient's medical record and in the AE section of the eCRF.

Once the patient is enrolled in the study, AEs will be collected from index date (i.e., date of treatment initiation with faricimab) until the end of his or her observation period. After this period, the HCP is not required to actively monitor patients for AEs; but if the treating HCP becomes aware of any related AEs to any medicinal product, they should be notified to the competent authority in the Member State where the reactions occurred or to the MAH of the suspected medicinal product, but not to both (to avoid duplicate reporting).

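### Section 6.7.3 splits ocular adverse events by drug but not non-ocular ones, so the systemic summary for faricimab, as written, mixes time on and off the drug

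*Protocol*

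**What the plan says.** Protocol Section 5.2.2 sets the aim: "To evaluate the ocular and systemic safety and tolerability for faricimab in nAMD and DME in the real-world setting".

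Section 6.7.3 then gives two different breakdowns in adjacent sentences. For systemic events: "Non-ocular AEs/serious adverse events (SAEs) will be assessed at patient-level, per cohort and per sub-cohort, for the SAS-PL". For ocular events: "Ocular AEs/SAEs will be assessed at eye-level, per faricimab and any other anti-VEGF treatment", and also by cohort and sub-cohort. The same section plans cumulative incidence and rates per 100 patient-years (or patient-eye years), and closes with "For all outcome measures, events with onset through end of study will be summarized at the final analysis".

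Other sections fix who is followed and for how long:

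- Section 6.5.2, on patients who stop or switch: "even if faricimab is not being received in either eye, the patient should continue to participate in this study", until the end of study participation.
- Section 8.1.2.1: "AEs will be collected from index date (i.e., date of treatment initiation with faricimab) until the end of his or her observation period".
- Section 6.7.1.1: one dose of faricimab is enough for the safety sets.
- Section 6.7: sub-cohort is set by treatment history when faricimab is started, so it does not change with later exposure.

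**The concern.** A systemic event can be tied to a drug mainly through its timing relative to exposure, and this single-arm study has no comparator to help. Yet the split by drug is written for eyes and not for patients. A patient who switches in both eyes at month 4 and has a myocardial infarction at month 22 on another product would, on the text as it stands, be counted in the same non-ocular summary as a patient injected throughout.

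At stake is how the systemic results can be read. If a risk exists only during exposure, off-drug follow-up dilutes it. If off-drug time carries more events, for example on another product, the pooled figure overstates the risk on faricimab. Ascertainment may also fall after a switch. Section 6.9 accepts that non-ocular events may be underreported at eye clinics, and Section 8.2 says that events for non-studied products are not actively solicited.

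**Working it through.** The protocol states no adverse event rate, stopping rate or exposure total, so there is no planned figure to reproduce. The check has two parts.

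**Reading the text.** Non-ocular events are broken down by cohort (indication) and sub-cohort (naïve or pre-treated at initiation). Neither tells current exposure. Section 6.7.3 states no on-treatment window and no censoring at last injection, switch or discontinuation. Follow-up and event collection run to the end of observation (Sections 6.5.2 and 8.1.2.1). Relationship to therapy is collected (Table 1), but Section 6.7.3 does not list it as a breakdown, and it could not correct a denominator.

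**Illustrative size.** Inputs from the protocol: about 850 patients and 2 years of follow-up (Section 6.1.1), so 850 × 2 = 1,700 patient-years before drop-out. Assumed inputs: a share q of patients stop faricimab in both eyes, on average at month m. The off-faricimab share is

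f = q × (24 − m − t)/24,

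where t is any tail after the last injection that is still counted as exposed. I take t = 0, or t = 16 weeks = 16 × 7/30.44 = 3.68 months. With r the off-drug rate divided by the on-drug rate, the pooled rate divided by the on-drug rate is (1 − f) + f × r.

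| q, m, t | f | Off-drug patient-years | Ratio at r = 0.5 | Ratio at r = 2 |
|---|---|---|---|---|
| 10%, 12, 0 | 0.10 × 12/24 = 5.0% | 85 | 0.975 | 1.050 |
| 10%, 12, 3.68 | 0.10 × 8.32/24 = 3.5% | 59 | 0.983 | 1.035 |
| 30%, 6, 0 | 0.30 × 18/24 = 22.5% | 383 | 0.888 | 1.225 |
| 30%, 6, 3.68 | 0.30 × 14.32/24 = 17.9% | 304 | 0.910 | 1.179 |

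At r = 1 the ratio is 1 in every row.

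With wider assumptions (q from 5% to 40%, m from 6 to 12 months, no tail), f runs from 0.05 × 12/24 = 2.5% (about 42 patient-years) to 0.40 × 18/24 = 30% (510). The ratio then runs from 0.85 to 1.30 for r between 0.5 and 2.

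Events are collected from the index date, which may be up to 3 months before enrolment, so total time could reach 850 × 2.25 = 1,912.5 patient-years. The shares move little: 30% stopping at month 6 gives 0.30 × 21/27 = 23.3%.

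**The case against.** The strongest reply is that this belongs in the SAP. Section 6.7 leaves detailed methodology there, Section 6.7.3 never defines patient-years, and nothing in it forbids an exposure split. The closing sentence on onsets through end of study can be read as a data-cut statement, in contrast with the annual interim analyses of Section 6.7.5. It also covers ocular events, which are split.

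There is also a reasonable explanation for the asymmetry, although the protocol does not give it. An eye has one injection history, whereas a patient may have two treated eyes with different drugs and start dates, so a drug label is less clean at patient level. An ever-exposed, all-follow-up summary is a legitimate display in a descriptive study. Finally, Section 6.7.2.2 reports discontinuation and switching by eye, which shows part of the off-drug share.

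Much of this stands, and it rules out some stronger readings:

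- A reader might infer that off-drug months certainly enter the denominator. That is only an inference from the absence of stated censoring.
- A reader might infer that the plan attributes other products' events to faricimab. It plans descriptive incidence in patients who received faricimab, not a causal estimate.
- A reader might take 16 weeks as the natural end of systemic exposure. The protocol names it as a treatment interval, not as a systemic risk window. It also allows other intervals and as-needed treatment (Appendix 5), so a strict 16-week cut would label some patients as stopped who have not stopped.

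The reply does not remove the point itself. The protocol did not leave the breakdowns open. It named them, and named the drug split for ocular events only, although the stated objective covers both kinds of event. Eye-level switch counts do not show when a patient was free of faricimab in both eyes, nor which events fell in that time.

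**Conclusion.** The point holds as a cheap improvement. As written, and with no censoring stated, the non-ocular summary mixes time on faricimab, time on another anti-VEGF and untreated time, while the objective is the systemic safety of faricimab.

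Its size and direction cannot be found from the documents. The range of about 3.5% to 22.5% of 1,700 patient-years rests on assumed stopping of 10% to 30% of patients in both eyes, at month 12 to month 6, with or without a 16-week tail. Over that range the pooled rate is about 0.89 to 1.23 times the on-drug rate if the off-drug rate is between half and double it.

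A reader might conclude that the plan will understate systemic risk. The documents do not support a direction: dilution, a higher off-drug rate and weaker ascertainment after a switch are all possible. The SAP, which was not available, may already contain an exposure split.

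**What to change.** In Section 6.7.3, keep the all-follow-up table and add non-ocular AE and SAE counts with patient-year rates by patient-level exposure period:

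- on faricimab in at least one eye;
- after faricimab has stopped in both eyes, divided into other anti-VEGF and no anti-VEGF.

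Flag time with another anti-VEGF in the fellow eye during the first period.

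State how the on-faricimab period ends. It can end at the recorded switch or discontinuation date in the last faricimab-treated eye, or at the last injection plus an analysis window that the sponsor pre-specifies, with one alternative window as a sensitivity analysis. Sixteen weeks may serve as such a window, as an analysis convention only. Patients with no recorded discontinuation stay in the on-faricimab period, so that long-interval and as-needed patients are not misclassified. Define patient-years at risk for each period in the same place.

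The cost is a short addition to Section 6.7.3 and a derived period flag. Dates of injections, switches, discontinuations and other treatments are already collected (Table 1), so no visit, treatment or data field changes. On-drug patient-years will be fewer than total follow-up, so those intervals will be slightly wider.
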